**A. INVESTIGATIONAL PLAN**

**Purpose**

Fractures of long bones constitute the majority of emergency operating room procedures in most trauma centers. Of these long bone injuries, tibial fractures are the most common. The National Center for Health Statistics reports an annual incidence of 492,000 fractures of the tibia and fibula per year in the United States. Patients with tibial fractures remain in the hospital for a total of 569,000 hospital days and incur 825,000 physician visits per year in the United States. Delayed fracture healing is a common complication associated with high-energy tibia fractures. Open tibia fractures with bone loss rarely unite without a secondary intervention. Delayed bone grafting of the defect is commonly used to provide stimulus for healing. The use of an autogenous iliac crest bone graft (ICBG) has remained the gold standard in the treatment of tibial non-unions with a bone defect. However, there are significant limitations to autogenous bone grafting, including the increased risk of infection from a second surgical incision and pain associated with the bone graft harvest site, which may range from 1-5 days to more than a year. Additional risks include iatrogenic fracture and damage to neurovascular structures. Also, not all patients are suitable donors. Relative contraindications to ICBGs include previous iliac crest harvesting; poor bone quality secondary to underlying disease, smoking or medications that affect the quality of bone; and advanced patient age. Finally, there is a finite amount of bone that may be obtained from the ilium, and it may not be adequate in all donors to address critical size defects. Recent technological advances with the advent of recombinant bone morphogenetic proteins emerging as a viable bone graft substitute may offer a viable alternative for patients.

The purpose of our study is to evaluate the use of one such recombinant protein in patients at a high risk for nonunion. We will evaluate open tibial shaft fractures treated with an intramedullary nail and a circumferential bone defect of at least one centimeter in length compromising at least 50% of the circumference of the bone. Patients with critical sized defects who undergo a planned, secondary grafting or whose fractures fail to demonstrate progression towards union over three consecutive months of radiographic and clinical evaluation will be included. Patients will be randomized to the use of recombinant human bone morphogenetic protein 2 (RhBMP-2) or standard ICBG to stimulate healing. The ability to restore skeletal integrity without the morbidity associated with bone graft harvesting would represent a major advantage for the patient. As a secondary evaluation, given that rhBMP-2 has been associated with decreased infections when used in open tibia fractures, we will also determine if patients with these severe fractures have a decreased infection rate with the use of rhBMP-2/ACS relative to the control group. In addition, the overall economic impact of the 2 treatment groups will be evaluated with a cost effectiveness evaluation.

**Research Question:**

*Primary:*

What is the relative effect of rhBMP-2/ACS versus autogenous ICBG on rates of union in patients with critical size defects following tibial shaft fractures?

## **IRB00003098 Funding Protocol rhBMP-2/ACS vs. Autograft for Critical Size Tibial Defects**

*Null hypothesis: rhBMP-2/ACS has the same union rate when used in critical-sized defects as does ICBG.*

*Secondary:*

What is the relative effect of rhBMP-2 versus autogenous ICBG on infection rates in patients with nonunion or critical size defects following tibial shaft fractures?

*Null hypothesis #2: The infection rate in open tibias with critical-sized defects treated with rhBMP-2 and autogenous ICBG are the same.*

What is the economic impact of the use of RhBMP 2 for tibial fractures with critical sized defects?

*Null hypothesis #3: There will be no difference in the economic cost of the treatment of critical sized defects using the RhBMP-2 versus iliac crest bone graft.*

This investigation is a prospective, stratified, parallel, randomized, blinded multicenter trial to evaluate the use of rhBMP-2/ACS in 25 patients versus a control group of 25 patients who have tibial fractures with critical size defects. A committee of orthopaedic surgeons will independently adjudicate our primary outcome, fracture healing at 12 months. Participating centers are part of the Major Extremity Research Consortium (METRC) and have experience with performing randomized clinical trials. Approval by each center's institutional review board will be obtained prior to commencing the study and we will follow the research guidelines set forth by each site.

### **Protocol**

The patients who provide informed consent will be randomized to one of two treatment groups: Patients in the control group (C) will not receive the rhBMP-2, but instead will be treated with an autogenous iliac crest bone graft. Patients in the treatment group (T) will receive 1.50 mg/ml -12 mg of rhBMP-2 soaked on an absorbable collagen sponge (rhBMP-2/ACS) as an adjuvant to a freeze-dried cancellous allograft. Each patient will be separately randomized via a computer-generated number at the Data Control Center. The grafting material for both groups will be surgically implanted on a delayed basis. For our study, patients will be bone grafted between six and sixteen weeks after the initial injury. In an acute fracture setting, autogenous bone graft is not indicated for at least the first six weeks as the factors present in the fracture hematoma and in the fracture region would lead to consumption of the autogenous bone graft. It is not appropriate for anyone to be considered for acute bone grafting in tibial shaft fractures until at least six weeks after the initial injury. Time intervals for the bone graft surgery are between six and sixteen weeks after injury with no evidence of fracture healing on the radiographs. In addition, sometimes the soft tissue injury which accompanied the tibial shaft fracture may be so extensive that even at 16 weeks it may not be an appropriate soft tissue envelope in order to operate through. We leave that to the discretion of the surgeons when it is safe for intervention to promote healing. However, if the patient's treatment plan does not include bone graft within 16

## **IRB00003098 Funding Protocol rhBMP-2/ACS vs. Autograft for Critical Size Tibial Defects**

weeks of injury, the patient will not be eligible to participate. The literature supports interventions for non union be considered after 6 months from injury. This will guard against enrolling patients with “non-unions”. Patients eligible for this study all had open fractures with bone defects. The soft tissue envelope needs to adequately recover from the original injury to be safe for additional surgery. Extending the window until 16 weeks permits time for adequate soft tissue recovery for the surgical procedures.

The case report form provides a space to record the size of the defect as measured from the AP and lateral x-rays. The measurement should be recorded as a total of the length, width and depth of the defect. Because an intramedullary nail is in place, the depth of the defect is to be recorded as the cortical thickness. In addition, there should be measurements made of the defect volume intra-operatively. The extent of the intra-operative defect will include area of bone loss >25% of the circumference to avoid measurement of small spikes that are clinically irrelevant. Intra-operative defect size will be recorded on case report forms.

The patients in the control group will undergo iliac crest bone graft surgery per the surgeon’s usual practice. The treatment group will be managed in a similar fashion, with the rhBMP-2/ACS placed at the site of bone defect on a collagen sponge carrier per manufacturer’s instructions. The patients will receive crushed cancellous allograft packed into the defect prior to an overlay of the rhBMP-2/ACS. The maximum amount of allograft chips is 60 cc to be used to fill the defect. The allograft chips will be loosely packed to fill the cortical defect flush to the cortical bone. After the allograft is implanted into the site and there is an adequate hemostasis, the RhBMP2 sponge will be applied as an overlay covering the allograft and bridging the proximal and distal tibial fragment of the defect; that is laying flat on the surface. The sponge is not to be folded, rolled or placed in any other configuration. The sponge requires no sutures to be held in place. If the patient requires more than one large pack of Infuse, they will be excluded from the study. This RhBMP2/ACS implant will be placed directly adjacent to viable muscle bed. A drain will not be used. Wound closure will commence when hemostasis is obtained. The amount of cancellous chips and brand used will be recorded on the case report form.

Medtronic Sofamer Danek markets rhBMP-2/ACS as INFUSE Bone Graft. They have agreed to provide kits of rhBMP-2 to the 25 patients randomized to the treatment group. This donation is unrestricted. Medtronic Sofamer Danek will not be a participant in the study, nor will have any access to patient or study data or any input into data analysis, results and presentations.

The patients in both groups will be evaluated at 2 weeks, 6 weeks, 12 weeks, 18 weeks, 6 months and 12 months. Outcome measures will be “union,” “wound healing and infection,” and “need for further intervention.” Pain will be documented using the Visual Analogue Scale (VAS) at each visit. Short Form-12 (SF-12) and the Short Musculoskeletal Functional Assessment (SMFA) will be completed at 6 months and 12 months. Billing information will be obtained at the end of the 12 month study period to estimate cost of care in both treatment groups.

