### **Consent Procedures**

## **IRB00003098 Funding Protocol rhBMP-2/ACS vs. Autograft for Critical Size Tibial Defects**

Written consent will be obtained during the clinic visit when bone graft surgery is scheduled. Prior to bone grafting procedure, female patients will be given a pregnancy test. Those with a positive pregnancy test will no longer be eligible and will receive standard treatment (iliac crest autograft). Patients with an active infection at the operative site, purulent drainage from the fracture or evidence of active osteomyelitis are not eligible for the study. Active infection will be defined clinically by skin changes, including redness, warmth and active drainage. Additionally, the diagnosis can be supported by laboratory values, including elevated WBC, ESR and CRP. Osteomyelitis is suspected by radiographic evidence of lytic lesions. If, at the time of surgery, the surgeon is concerned that the patient has a deep wound infection because of intra-operative findings that may include loose hardware, purulence or an inflammatory tissue reaction – the patient will be excluded from the study.

Informed consent will be obtained before any study procedures are initiated. The consent form will be reviewed in its entirety with the patient by the surgeon and research coordinator and all questions will be answered. Investigators will ask the subject questions to assure understanding before the consent for participation in the study is signed, specifically:

1. Can you explain what it means to be involved in this study?
2. What should you do if you no longer want to participate in the study?

If the patient cannot answer these questions, the patient will be deemed by the investigator to be incapable of providing informed consent secondary to a lack of mental competence; the subject will not be enrolled into the study.

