### **Inclusion/Exculsion Criteria**

#### Criteria For Inclusion Of Subjects:

- Patients 18-65 years old with an open tibia fracture involving diaphysis (if patient has a bilateral tibia fracture and both require a bone graft, then each will be randomized separately).
- Tibia fractures with a circumferential bone defect of at least one centimeter in length compromising at least 50% of the circumference of the bone.
- The definitive treatment of the tibia fracture must be with an intramedullary nail (may have temporary external fixation prior to IM nail placement).
- Patients whose treatment plan includes placement of a bone graft between 6 to 16 weeks after their initial injury.
- Patients who have no evidence of infection by clinical examination (defined as active infection at the operative site, purulent drainage from the fracture or evidence of active osteomyelitis at the time of bone graft).
- Patients who are independent in living and ambulation prior to injury.
- Patients who are English speaking.
- Patients who are willing to provide consent and available for follow-up for at least 12 months following definitive surgical procedure.

Criteria For Exclusion Of Subjects:

- Patients who are pregnant or lactating.
- Patients with known hypersensitivity to rhBMP-2 or bovine type I collagen.
- Patients with a history of tumor, a resected or extant tumor, an active malignancy, or patients undergoing treatment for malignancy.
- Patients who are skeletally immature (<18 years of age or no radiographic evidence of epiphyseal closure).
- Patients with inadequate neurovascular status, e.g. high risk of amputation.
- Patients with compartment syndrome of the affected limb.
- Patients with immune deficiency or history of auto-immune disease,
- Patients who have undergone treatment of any other investigational therapy within the month preceding implantation or planned within the 12 months following implantation.
- Patients unable to return for required follow-up visits.
- Patients who have medical co-morbidities that preclude treatment with a general anesthetic.
- Patient who is pending incarceration or who is incarcerated.
- Patients with an active infection at the operative site defined clinically by skin changes including redness, warmth and active draining, purulent drainage from the fracture or evidence of active osteomyelitis based on radiographic evidence of lytic lesions at the time of bone grafting.

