- Patient has segmental defects longer than 5cm in length as measured on AP and lateral radiographs of the injury taken after the final debridement following internal fixation
- Patient has a segmental defect longer than 6cm as measured intraoperatively after debriding .
- Patients who have segmental defects that require more than 60 cc of bone graft.
- Patients who require more than one large kit of rhBMP-2 at time of surgery.
- Patient's anticipated treatment plan also includes the use of other procedures to promote fracture healing, e.g. ultrasound, magnetic field or electrical stimulation.
- Patient's tibia fracture has been treated with additional fixation beyond the intramedullary nail, e.g. plates, wires or screws, and additional surgical fixation, e.g. fibulectomy, exchange nail and dynamization of locked nail
- Patients who have pathological fractures; a known history of Paget's disease or known history of heterotopic calcification.
- Patients with a Glasgow Coma Scale less than 15 (less than fully awake) at the time of informed consent.
- Patients with previous hardware in place that prevents placement of an intramedullary nail for treatment of the tibial shaft fracture.
- Patients with prior use of INFUSE.

*If the patient is a female of child bearing potential:*

- Does she have a negative pregnancy test (administered within 72 hours prior to surgery)?
- Has she agreed to use adequate contraception for a period of at least 1 year following implementation of rhBMP-2?

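### The plan excludes patients for findings at surgery without saying whether they have already been randomised; if they have, the exclusions conflict with the intent-to-treat analysis

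*Combined protocol and SAP*

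**What the plan says.** **Order of consent and randomisation.** Consent Procedures: "Written consent will be obtained during the clinic visit when bone graft surgery is scheduled". Protocol: "The patients who provide informed consent will be randomized to one of two treatment groups". Number of Sites/Investigators/Patients describes central, web-based block randomisation but gives no time of release relative to surgery.

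**Exclusions that depend on surgery.**
- Kit limit, in the treatment-group procedure under Protocol: "If the patient requires more than one large pack of Infuse, they will be excluded from the study". The exclusion criteria repeat it: "Patients who require more than one large kit of rhBMP-2 at time of surgery".
- Suspected deep infection, in Consent Procedures: "If, at the time of surgery, the surgeon is concerned that the patient has a deep wound infection because of intra-operative findings". Such a patient is excluded from the study.
- The exclusion criteria also list a segmental defect over 6 cm measured intra-operatively and a need for more than 60 cc of graft. No time is given for the second, but it may be known only at grafting.
- The infection criterion for inclusion is dated to surgery as well: "evidence of active osteomyelitis at the time of bone graft".

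**Eligibility can lapse after consent.** On pregnancy testing before the graft procedure, Consent Procedures says: "Those with a positive pregnancy test will no longer be eligible and will receive standard treatment (iliac crest autograft". That gives the treatment, but not whether the patient is followed, counted or analysed.

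**Analysis.** Final Analysis requires intent to treat, with each patient kept in the randomised group. It names no exception and no modified population.

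**The concern.** Consent comes before the day of surgery, and the kit rule stands among the treatment-group operative steps. Both make it plausible that the arm is known before these rules are applied. Removing patients from the study would then empty the intent-to-treat set of people it is meant to contain.

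The rules are not equally serious. The infection, 6 cm and 60 cc rules are worded the same for both arms and could bias the comparison only through judgement made with the arm known. The kit rule concerns a product that only one arm receives, so after allocation it can remove rhBMP-2 patients only, probably those with larger defects. If larger defects unite less often, their loss would favour rhBMP-2.

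The supplied text does not say whether an excluded patient is followed or replaced. The kit donation is described by number randomised ("They have agreed to provide kits of rhBMP-2 to the 25 patients randomized to the treatment group"), which does not settle replacement. If removed patients are not followed, no later analysis can restore the randomised comparison. With 25 per arm, each removal is 4% of an arm.

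**Working it through.** **1. The plan's own sample size.** Inputs from Sample Size Justification: control healing 65%; rhBMP-2 20 points higher, so 85%; power 80%; alpha 0.05, taken as one-sided; margins 10 and 20 points.

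n per arm = (1.645 + 0.842)² × (0.65×0.35 + 0.85×0.15) / (0.20 + margin)²

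- Margin 10 points: 6.183 × 0.355 / 0.09 = 24.4, so 25.
- Margin 20 points: 6.183 × 0.355 / 0.16 = 13.7, so 14.

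Both stated figures are reproduced. One-sided 0.025 would give 31 and 18, so the plan's size rests on one-sided 0.05.

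**2. Power if patients are lost from the rhBMP-2 arm.** Power = Φ(0.30/SE − 1.645), with SE = √(0.1275/n_B + 0.2275/25).

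- 25 v 25: SE 0.1192, power 80.9%.
- 24 v 25: SE 0.1201, power 80.3%.
- 23 v 25: SE 0.1210, power 79.8%.

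Power is not the issue.

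**3. One-sided removal and false non-inferiority.** Assumptions not in the documents: true union 55% with rhBMP-2 against 65% control (exactly at the 10-point margin); a fraction f of the rhBMP-2 arm removed, 4% (one of 25) or 8% (two of 25); union q among those removed, 20% or 40%. Final Analysis names no non-inferiority test, so a Farrington–Manning test at one-sided 0.05 is assumed. Its rejection probability is computed exactly, by summing binomial probabilities over all outcomes.

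Apparent rhBMP-2 rate = (0.55 − f×q)/(1 − f). For example, (0.55 − 0.08×0.20)/0.92 = 0.580.

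| Removed | q | Apparent rate | False non-inferiority, 25 v 25 analysed |
|---|---|---|---|
| none | – | 0.550 | 4.5% |
| 4% | 0.40 | 0.556 | 5.0% |
| 4% | 0.20 | 0.565 | 5.7% |
| 8% | 0.40 | 0.563 | 5.5% |
| 8% | 0.20 | 0.580 | 7.1% |

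If those removed are not replaced, compare with the same arm sizes without selection:
- 24 v 25: 5.9–6.6%, against 5.4%.
- 23 v 25: 6.1–7.8%, against 5.0%.

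Selection alone therefore adds about 0.5–1.2 points (one removed) or 1.1–2.7 points (two removed).

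**4. Equal removal from both arms.** Applying the same formula to the control rate gives 4.0–4.3%, so there is no inflation. Only one-sided removal matters.

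**5. The test the plan names.** Final Analysis specifies Fisher's exact test. With both arms truly at 65% and 25 v 25 analysed, the chance of a significant result favouring rhBMP-2 is:
- 1.3% with no removal;
- 1.6–1.8% with 4% removed;
- 1.9–2.53% with 8% removed.

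The nominal one-direction rate is 2.5%.

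**6. What strict intent to treat costs.** Suppose a fraction g of each arm gets neither study graft and unites equally (at 20–60%). The true deficit shrinks to (1 − g) × 10 points: 9.6 at g = 4% and 9.2 at g = 8%. False non-inferiority becomes 4.8% and 5.0–5.1%, against 4.5%.

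**The case against.** The strongest reply is that there may be no conflict. The kit, 6 cm and 60 cc limits are listed as exclusion criteria for all subjects, and infection status is dated to the time of grafting. Criteria dated to surgery fit allocation after those checks. The Protocol section fixes only that randomisation follows consent, and a web system can release an allocation in theatre. The position of the kit rule proves little, because eligibility rules are scattered through the narrative: the 16-week rule is under Protocol, and the pregnancy and infection rules are under Consent Procedures. This stands, and it is why the point is conditional. It does not remove the need to state the order, since up to 22 sites could otherwise follow different sequences.

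The kit rule may also seldom operate. A patient must first pass the 5 cm, 6 cm and 60 cc limits, which apply to both arms. The sponge is 7.5 × 10 cm (Device Description), and Bone Grafting Procedure asks for coverage only as far as the opening allows. This stands too: the frequency is unknown and probably low.

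Finally, Final Analysis already says how randomised patients are to be analysed. That is partly right. What remains is that two sections exclude such patients from the study, with nothing on follow-up or replacement. An intent-to-treat rule cannot be carried out on outcomes that were never collected.

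Two parts of the document, after Monitoring Procedures and after the adverse-event reporting plan, were not available. The statements about what is missing are limited to the rest.

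**Conclusion.** The point holds as a conditional one. If allocation precedes surgery, the exclusions under Protocol and Consent Procedures, read plainly, remove randomised patients and conflict with Final Analysis; the kit rule would then act on the rhBMP-2 arm alone. If all checks are completed first, there is no conflict and only the statement of order is missing.

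A reader might infer that the plan flatly contradicts itself, or that the comparison will be materially biased towards rhBMP-2. The documents support neither. They do not establish that allocation comes first, they give no exclusion rate, and the calculated effect is small: 4.5% rising to 5.0–7.1% with 25 v 25 analysed, up to 7.8% at 23 v 25, and Fisher's test barely above nominal at worst. All of this rests on assumed removal and union rates and, for non-inferiority, on an assumed test.

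It should still be fixed, because a one-sided loss without follow-up cannot be recovered and preventing it is cheap. Confidence is medium.

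**What to change.** **Needed.**
- For any patient already randomised, replace exclusion from the study (Protocol and Consent Procedures) with follow-up to 12 months and inclusion in the intent-to-treat analysis in the randomised arm.
- Report ineligibility found at surgery by arm, with reasons.
- State when allocation is released relative to the intra-operative checks, and reconcile Protocol, Consent Procedures, the exclusion criteria and Final Analysis.

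**Optional.**
- A supportive per-protocol analysis, since the trial is sized for non-inferiority and intent to treat can dilute a true deficit. Read it with the counts by arm, because it carries any one-sided removal.
- Release of allocation in theatre through the existing web system, after eligibility has been judged for every patient. This needs both graft routes ready for every patient, including iliac harvest and allograft chips, and a way of judging the kit limit before the arm is known.

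**Cost.** Wording, 12-month follow-up of the few patients concerned, and slight dilution under intent to treat (4.5% to 4.8–5.1% in the illustration). No extra patients are needed, and no clinical limit or surgical step changes.
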